 10. Have a reliable and competent trial partner (eg, spouse, family member, or other caregiver) who meets the following requirements and trial obligations (see Section 7.1.5.1 for source documentation information):
 - Signs their own informed consent, after the trial has been explained to them, and before Screening assessments.
 - Is not diagnosed with dementia.
 - Resides with the subject overnight (see Section 7.1.5 for more details) and has a close relationship with the subject (defined as daily face-to-face contact, at least 15 waking hours a week for at least 3 months prior to Visit 1).
 - Accompanies the subject to and from trial visits and willing to stay overnight at the sleep laboratory, if needed, for the 3 PSG visits (See Section 7.1.5 for

more details regarding flexibility for alternate caregivers to accompany the subject on clinic visits and overnight PSG visits).

- Assumes responsibility for trial medication procedures (eg, witnessing and/or helping to administer trial medication, assessing compliance), for completion of the sleep e-diary each morning, and oversight of the activity/sleep watch worn throughout the trial.
 - Answers questions regarding the trial partner's sleep quality and trial partner's distress related to the subject's behaviors.
11. Have results of clinical laboratory tests (complete blood count [CBC], blood chemistries, thyroid function tests, and urinalysis) within normal limits or clinically acceptable to the investigator at Screening.
12. Have results of a physical examination (PE), including neurological exam, vital signs, and ECG (Bazett's correction) within normal limits (based on the population under study, ie Alzheimer's disease and insomnia) or clinically acceptable based on investigator judgment at Screening.
13. If female, not be of childbearing potential as indicated by one of the following:
- Has reached natural menopause, defined as ≥ 45 years of age with either:
 - i. ≥ 12 months of spontaneous amenorrhea
 - or
 - ii. ≥ 6 months of spontaneous amenorrhea with serum follicle stimulating hormone (FSH) levels >40 IU/L as determined by the central laboratory
 - Has had a hysterectomy;
 - Has had bilateral tubal ligation; or
 - Has had a bilateral oophorectomy (with or without a hysterectomy) and greater than 6 weeks have passed since the surgery
14. Be willing to provide a blood sample for APOE genotyping.

Visit 2: Screening PSG Inclusion

Note: Continue to fulfill relevant Inclusion Criteria at Visit 1.

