Concomitant medications should be collected during the post-treatment follow-up phone call in the event an AE is reported.

Table 3 Allowed Medications, Supplements, and Other Substances (non-inclusive list)

Medication Category	Examples*/ Notes (*specific medications listed are examples of class compounds and are not limited to those listed)
AD medications	eg, donepezil, galantamine, memantine, rivastigmine Note: Subject must be on a stable dose for at least 1 month prior to Screening Visit.
Antidepressants	eg, SSRI and SNRI medications, including bupropion, citalopram, escitalopram, fluoxetine, mirtazapine, paroxetine, sertraline, venlafaxine
Antihistamines: Non-sedating	Note: Non-sedating antihistamines are not to be taken more than twice a week. Note: Montelukast sodium (SINGULAIR™) and inhaled corticosteroids may be used more than twice weekly as needed for allergic symptoms
Antipsychotics	eg, aripiprazole, asenapine, olanzapine, risperidone, ziprasidone Note: quetiapine is allowed if used on an as needed basis for daytime control of neuropsychiatric symptoms, but quetiapine is prohibited if used for sleep. Subjects should avoid taking quetiapine for at least 3 hours before going to bed throughout the duration of the study, and refrain from using quetiapine, for at least 24 hours before, and during, PSG visits.

Product: MK-4305
Protocol/Amendment No.: 061-01

Medication Category	Examples*/ Notes (*specific medications listed are examples of class compounds and are not limited to those listed)
Centrally acting analgesics	eg, codeine, hydromorphone, morphine, oxycodone, propoxyphene, and its variations, & combination products that contain a narcotic. May be taken as needed for pain relief (with the documented approval of the Merck clinical monitor), but use may not exceed 3 consecutive days or >4 days per any week. Note: Use of narcotics for pain relief should be avoided if there are effective alternative therapies such as non-steroidal anti-inflammatory agents. Sponsor must be notified of any use exceeding 3 consecutive days or >4 days per any week.
Muscle relaxants (centrally acting with psychotropic effects)	eg, methocarbamol Note: Use of centrally acting muscle relaxants should be avoided if there are effective alternative therapies such as non-steroidal anti-inflammatory agents. Sponsor must be notified of any use exceeding 3 consecutive days or >4 days per any week.

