6.0 TRIAL FLOW CHART

	Screening Period					Treatment Period			Discontinuation	Post-Treatment
	1	Placebo Run-in		3	4	5	6			
Visit Number/Title:	Screening ^{a, b}	2	3	4	5	6		Discon	Follow-up TC ^d	
Scheduled Week/Day	Day -21	Day -14/-13	Day-7/-6	Day 1	Day 15	Day 29/30			14 days Post-dose	
Scheduling Window by Days:	+28 ^e	-3/+3 ^f	-3/+4	-3/+3	-3/+5	-3/+5			+2	
Administrative Procedures		PM ^g	AM	PM ^g	AM			PM ^g	AM	
Informed Consent – Subject	X									
Informed Consent – Trial partner	X									
Informed Consent – Future Biomedical Research (FBR)	X									
Inclusion/Exclusion Criteria	X	X	X	X	X	X ^h				
Subject Identification Card	X									
Medical History	X									
Prior Medication Review	X									
Concomitant Medication Review	X	X		X	X	X	X	X	X	X
Monitor Trial Medication Compliance				X	X	X	X	X	X	
Call/Log-in to IVRS/IWRS	X	X			X	X ⁱ		X	X	
Dispense Trial Medication to Subject/Trial partner		X ^j			X	X ⁱ				
Site Witnessed Trial Medication Dose prior to PSG		X		X				X		
E-diary Training	X									
E-diary monitoring ^k	X	-----X						X	X	
Activity/Sleep Watch Training		X								
Activity/Sleep Watch monitoring ^l		X-----X								
Clinical Procedures/Assessments		PM	AM	PM	AM			PM	AM	
AD Diagnosis: NIA-AA or DSM-5 criteria ^m	X									
Mini-Mental State Examination (MMSE) ⁿ	X					X		X	X	
Modified Hachinski Ischemia Score (MHIS)	X									
Insomnia Diagnosis: DSM-5 criteria ^m	X									
Insomnia Diagnosis: Insomnia Diagnostic Interview (IDI) ^m	X									
Insomnia Diagnosis: Sleep History (SHX) ^m	X									
15-item Geriatric Depression Scale (GDS)	X									
Neuropsychiatric Inventory (NPI)						X		X	X	
Clinical Global Impression – Severity (CGI-S), for insomnia						X	X	X	X	
Columbia-Suicide Severity Rating Scale (C-SSRS) - Screening	X									
Columbia-Suicide Severity Rating Scale (C-SSRS) - Since Last Visit			X		X	X	X	X	X	X ^o

	Screening Period					Treatment Period				Discontinuation	Post-Treatment	
	Placebo Run-in											
Visit Number/Title:	1 Screening ^{a, b}	2 Screening PSG		3 Baseline PSG		4 Rand ^c	5 End of Week 2	6 End of Week ^{cc} 4 - PSG		Discon	Follow-up TC ^d	
Scheduled Week/Day	Day -21	Day -14/-13		Day-7/-6		Day 1	Day 15	Day 29/30			14 days Post-dose	
Scheduling Window by Days:	+28 ^e	-3/+3 ^f		-3/+4		-3/+3	-3/+5	-3/+5			+2	
Digit Symbol (DS) ^p					X				X	X		
Polysomnography (PSG)		X		X				X				
Neurological Examination (NE)	X							X		X		
Physical Examination (PE)	X							X		X		
12-Lead Electrocardiogram (ECG)	X								X	X		

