Subjects/Trial partners will return for their final in-clinic/overnight visit, Visit 6 End of Week 4 PSG. Subjects/Trial partners will be instructed to arrive at the sleep lab approximately 2 hours prior to their median habitual bedtime as calculated at Visit 3 Baseline PSG. Subjects/Trial partners should be advised to eat dinner prior to arrival at the sleep lab and subjects should be reminded to refrain from alcohol, caffeine, and nicotine as recommended in Section 5.7.2.

Subjects/Trial partners should be instructed to bring all trial supplies (eg, e-diary, activity/sleep watch, trial medication) to the site for final compliance and accountability. The subject should still be wearing the activity/sleep watch until completion of the PSG the following morning.

Visit 6 PSG and associated assessments are to be conducted at the PSG center the night of (ie, alcohol breath test, UDS, witnessed dose of trial medication) or the morning after (ie, DS and PK sampling) completion of the PSG. Safety and ancillary assessments (eg, ECG, labs, vital signs, physical exam, neurology exam, CGI-S, NPI, or C-SSRS, etc) may be completed as noted in the Trial Flow Chart either on the day of the PSG PM Visit (Target Day 29) or PSG AM Visit (Target Day 30) to provide flexibility for subjects and trial partners that need to travel between the primary research site and a PSG center or to assist site staff with scheduling.

For trial medication dosing, please refer to Section 5.2.1.2. For urine drug screen and alcohol breath test details, please see Sections 7.1.3.1.2 and 7.1.2.2.14.3 , respectively.

The PK sample taken at this visit should be drawn between 8.5 to 11 hours post-dosing of trial medication on the AM portion of the visit.

The PSG recording for this visit does not need to be scored by the site. The Visit 6 PSG recording will be forwarded directly to the Central PSG Reader for scoring.

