8.4.4 Derivations of Safety Endpoints

Cataplexy and sleep-onset paralysis are defined as ECIs in this study which will be adjudicated by an independent, external CAC. Falls/ataxia/worsening of balance will also be evaluated as part of this adjudication process to rule out cataplexy. The adjudicated events will be evaluated as Tier 1 events as part of the tiered analysis strategy (see Section 8.6.2). Specific adverse experience terms relating to these ECIs will be identified and confirmed as part of the adjudication process prior to final study unblinding. Other Tier 1 events (eg, selected events associated with potential for abuse and complex sleep-related behaviors) that consist of multiple AE terms will be defined separately prior to unblinding.

Changes from baseline during the treatment period will be evaluated for laboratory, vital signs, and ECG data in accordance with predefined criteria noted Appendix 12.13.

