12.13 Predefined Limits Of Change Criteria

Table 1

Predefined Limits of Change Criteria for Laboratory Data

Laboratory Test	Criteria [†] as a % of a Limit of Normal Range
Hematology	
Hematocrit (M)	≤94.9% LLN
Hematocrit (F)	≤94.1% LLN
Hemoglobin (M)	≤90.5% LLN
Hemoglobin (F)	≤81.9% LLN
WBC	≤64.2% LLN ≥149.0% ULN
Neutrophils	≤37.0% LLN
Eosinophils	≥147.0% ULN
Platelets	≤57.7% LLN ≥177.7%ULN
Hepatic Function	
Bilirubin	≥166.7% ULN
Alkaline Phosphatase	≥300% ULN
AST (SGOT)	≥300% ULN
ALT (SGPT)	≥300% ULN
Renal Function	
Creatinine	≥142.9% ULN
Clinical Chemistry	
Sodium	≤94.7% LLN ≥105.4% ULN
Potassium	≤88.2% LLN ≥111.1% ULN
[†] A laboratory value must represent a worsening from baseline (ie, be more abnormal in the direction of interest) to meet the definition. LLN=Lower limit of normal. ULN=Upper limit of normal.	

Table 2

Predefined Limits of Change Criteria for Vital Signs,
 Weight, and Temperature

Measurement	Criteria
Systolic blood pressure	≥ 180 mm Hg and ≥ 20 mm Hg increase from baseline
	≤ 90 mm Hg and ≥ 20 mm Hg decrease from baseline
Diastolic blood pressure	≥ 105 mm Hg and ≥ 15 mm Hg increase from baseline
	≤ 50 mm Hg and ≥ 15 mm Hg decrease from baseline
Pulse	≥ 120 bpm and ≥ 15 bpm increase from baseline
	≤ 50 bpm and ≥ 15 bpm decrease from baseline
Orthostatic blood pressure	> 20 mm Hg systolic sitting to standing after treatment (but not in baseline)
Weight	$\geq 7\%$ increase from baseline
	$\geq 7\%$ decrease from baseline
Temperature	$\geq 101^\circ\text{F}$ and $\geq 2^\circ\text{F}$ increase from baseline ($\geq 38.3^\circ\text{C}$ and $\geq 1^\circ\text{C}$ increase from baseline)

Table 3

Predefined Limits of Change Criteria for ECGs

Measurement	Criteria
QTc Interval [†]	Prolongation compared to baseline ≥ 30 to ≤ 60 msec
	Prolongation compared to baseline > 60 msec
	Value ≥ 500 msec [‡]
[†] Correction based on Bazett's formula. [‡] The QTc Interval value must also represent a worsening compared to baseline to meet the definition.	

12.14 Mapping Between the 11 Categories of Suicidal Ideation and Behavior, the C-SSRS, and CDR for Programming Standard Tables

Table 1

Mapping Between the 11 Categories
 of Suicidal Ideation and Behavior and the C-SSRS

Category	C-SSRS Question (from eCRF) [†]
Suicidal ideation	
Passive	1. Wish to be dead
Active - nonspecific (no method, intent, or plan)	2. Non-specific active suicidal thoughts

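### The QTc limits of change rest on Bazett's correction alone, so a heart-rate change between the screening and Visit 6 ECGs can move subjects across the 30 msec limit; add Fridericia rows beside the Bazett rows

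*Combined protocol and SAP*

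**What the plan says.** Section 8.4.4 states: "Changes from baseline during the treatment period will be evaluated for laboratory, vital signs, and ECG data in accordance with predefined criteria", and points to Appendix 12.13. Table 3 of that appendix lists three QTc criteria: "Prolongation compared to baseline ≥ 30 to ≤ 60 msec", "Prolongation compared to baseline > 60 msec", and a value of at least 500 msec that is also worse than baseline. One footnote governs all three: "Correction based on Bazett's formula". Inclusion criterion 12 uses the same correction: "vital signs, and ECG (Bazett's correction) within normal limits". The documents name no second correction, no heart-rate adjustment and no QTc sensitivity analysis.

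The flow chart (Section 6.0) schedules ECGs at Visit 1, Visit 6 and Discontinuation. Footnote c makes the pre-dose Visit 4 assessments the baseline, but no ECG is scheduled at Visit 4, so the change in QTc has to be taken from the screening ECG. The chart puts the Visit 6 ECG in the morning column. Footnote cc and Section 7.1.5.2 relax this and allow it "either on the day of the PSG PM Visit (Target Day 29) or PSG AM Visit (Target Day 30". ECG conduct is left to a separate vendor manual (Section 7.1.2.1.2).

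Under Section 8.6.2, a limit of change met by at least 4 subjects in a group falls in Tier 2 and gets a between-group difference with a 95% interval. Otherwise it falls in Tier 3 and is shown descriptively. Neither tier carries a p-value.

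**The concern.** Bazett divides QT by the square root of RR. If QT shortens less than that as the heart speeds up, Bazett QTc rises with heart rate and falls when it slows, although repolarisation has not changed. The change criteria compare one screening reading with one reading about seven weeks later (Day -21 to Day 29/30), and the screening window allows up to 28 days more. Any heart-rate difference within a subject between those two readings enters the change directly.

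A fall in heart rate can pull a true prolongation under 30 msec, and a rise can create a false one. The pulse limits in Table 2 of the same appendix would not flag such shifts. They need a change of at least 15 bpm together with a pulse of at least 120 or at most 50. Safety is a primary objective (Section 3.1), and the number of subjects meeting a limit decides whether an interval is reported at all.

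**Working it through.** The plan gives no heart rate, expected heart-rate shift or QTc error, so there is no figure to reproduce. The size has to be computed under stated assumptions.

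**Inputs.** From the plan: Bazett's correction, the 30 msec limit and the 4-subject rule. Assumed: corrected QT of 420 msec, true QT proportional to RR^e with e = 1/3 or 0.40, and the heart rates shown. RR in seconds is 60/HR.

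**Formula.** QTcB = 420 × RR^e / RR^0.5 = 420 × (HR/60)^(0.5 − e). The spurious change is QTcB at Visit 6 minus QTcB at Visit 1.

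| Heart rate, Visit 1 to Visit 6 | e = 1/3 | e = 0.40 | Share of 30 msec |
|---|---|---|---|
| 75 to 62 bpm | −13.6 msec | −8.1 msec | 45% to 27% |
| 60 to 75 bpm | +15.9 msec | +9.5 msec | 53% to 32% |
| 70 to 60 bpm | −10.9 msec | −6.5 msec | 36% to 22% |

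Over these cases the error is 6.5 to 15.9 msec, which is 22% to 53% of the limit.

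**A true 30 msec prolongation.** Let corrected QT go from 420 to 450 msec while heart rate falls from 75 to 62 bpm. At e = 1/3, QTcB goes from 435.9 to 452.5, a change of 16.6 msec. At e = 0.40 it goes from 429.5 to 451.5, a change of 22.0 msec. Neither reaches 30.

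**Smaller shifts.** With e = 1/3, corrected QT 390 to 440 msec and baseline heart rate 55 to 75 bpm, a 5 bpm change gives 4.4 to 6.8 msec (15% to 23% of the limit).

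**Dependence on the exponent.** For 65 to 75 bpm at 410 msec, the error is 15.2 msec at e = 0.25, 10.0 at 1/3, 6.0 at 0.40 and 0 at 0.50.

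**Effect on counts (illustrative only).** This simulation assumes no drug effect, a cube-root relation, baseline heart rate of mean 67 (SD 9) bpm, SD of heart-rate change 8 bpm, corrected QT of mean 410 (SD 18) msec, and SD of true QTc change 12 or 15 msec. The expected count is the share with a change of at least 30 msec times 130 subjects per arm.

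| Correction, mean heart-rate shift | Share ≥30 msec | Expected per arm |
|---|---|---|
| Fridericia, any shift | 0.6% to 2.3% | 0.8 to 3.0 |
| Bazett, 0 bpm | 2.0% to 4.1% | 2.7 to 5.3 |
| Bazett, +10 bpm | 8.2% to 12.0% | 10.7 to 15.6 |
| Bazett, −10 bpm | 0.3% to 1.0% | 0.4 to 1.2 |

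These expected counts fall on both sides of the 4-subject cutoff, and the same shares apply to both arms.

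**The case against.** A reader might infer that heart rate differs systematically between the two visits. The documents do not show this. The Visit 6 ECG may be recorded in the evening or the morning, and the vendor manual may standardise rest and position. The Alzheimer's drugs allowed in Table 3 of Section 5.5 ("eg, donepezil, galantamine, memantine, rivastigmine") must be stable for a month before Visit 1 and should not change during the trial unless medically necessary. A drug taken steadily at both ECGs creates no difference between them. A shift is possible, not shown to be likely.

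A reader might also infer that the suvorexant-placebo comparison is biased. Allocation is 1:1 and blinded, with one ECG schedule, so a visit effect falls on both arms alike. Vital signs, including heart rate, are taken at every visit and summarised by arm, so a treatment effect on heart rate would probably be noticed. The QTc output is descriptive and touches no hypothesis test.

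The strongest objection is to replacing Bazett. At e = 0.40 Fridericia also errs, in the opposite direction: for 75 to 62 bpm at 420 msec it gives +5.3 msec against Bazett's −8.1. The two errors are about equal near e = (1/3 + 1/2)/2 ≈ 0.42, and above that Bazett is the less biased. The documents do not settle the exponent, so they do not support making Fridericia the main criterion.

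All of this stands. It limits the claim but leaves untouched the fact that one correction, with a known dependence on heart rate, is the only one planned.

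**Conclusion.** The point holds as a modest weakness in a descriptive safety display. With Bazett alone, a 10 to 15 bpm change between the Visit 1 and Visit 6 ECGs moves QTc by about 6.5 to 16 msec if the true exponent is 0.33 to 0.40 and corrected QT is 420 msec. A 5 bpm change moves it by about 4 to 7 msec under a cube-root relation, and at an exponent of 0.50 there is no error. Both the heart-rate shift and the exponent are assumptions, so no fixed share of the 30 msec limit can be stated as a property of this trial.

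The consequence is misclassification in both arms and a QTc row whose tier can depend on heart rate. Between-arm bias would require a treatment effect on heart rate, which the documents do not quantify. The primary and secondary efficacy analyses are unaffected.

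**What to change.** Before unblinding, add rows to Appendix 12.13, Table 3 that apply the same three criteria to Fridericia-corrected QT (QT divided by the cube root of RR) from the same ECGs. Keep the Bazett rows, which match inclusion criterion 12. Summarise ECG heart rate by visit and treatment arm, so that a disagreement between the two corrections can be interpreted. Fixing this in advance avoids a post hoc choice of correction.

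The cost is a few table rows, with no new ECG and no change to any test. Two QTc results may disagree and will need a sentence of explanation. The change assumes that QT and RR (or heart rate) are available in the ECG data; the documents do not say so, but Bazett's formula already needs both.
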